Military Benefit: Combat and combat-related joint injuries account for more than \$3 billion in aggregate financial costs. Outcomes for surgical interventions to repair articular fractures and ligament ruptures are quite good in short term follow-up studies. However, there is currently little that can be done to prevent/mitigate the development of PTOA following articular fracture and/or ligament injury long term. Thus, often the only option is joint replacement in a relatively young patient population. Our proposed interventions provide a vital surgical option for injured joints of military personnel, which addresses the risk of PTOA while still maintaining future surgical options if necessary.

2. Trial Objectives and Purpose

Evaluate safety and efficacy of unicompartmental biologic arthroplasty of the knee in a limited clinical trial.

With IRB approval, a limited pilot study will be performed to assess safety and efficacy of biologic unicompartmental arthroplasty. Ten patients who require tibial plateau and meniscus arthroplasty plus a femoral condyle arthroplasty, based on physical examination, radiographs, and knee arthroscopy, will be enrolled. Range of motion, VAS pain score, SF-12, Tegner score, International Knee Documentation Committee (IKDC) subjective and objective scores, PROMIS Bank v1.2 – Physical Function-Mobility, PROMIS v1.1 – Global Health, PROMIS Bank v1.1- Pain Interference, PROMIS Bank v1.2 – Physical Function, and Marx score as well as complete radiographs of the affected knee will be obtained prior to surgery and at 6 weeks, 3 months, 6 months, and 12 months after surgery to evaluate healing, function and evidence for arthrosis. We will document all complications, including joint or incision infection, graft failure, hardware failure, and arthrophibrosis. Patients with a VAS pain score >5 beyond 3 months postoperatively or clinical or radiographic evidence for nonunion or graft collapse will undergo MRI of the knee to determine the appropriate clinical course of action.

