Inclusion Criteria:

1. Patient requiring repair via tibial plateau and meniscus arthroplasty plus a femoral condyle arthroplasty
2. The subject is able and willing to consent to participate in the study

Exclusion Criteria:

1. Acute injury to any other part of the affected lower extremity
2. The subject is unwilling, or unable to consent due to psychiatric condition or legal incompetence
3. BMI > 40
4. Age > 50 at the time of enrollment
5. The subject is either pregnant, or a prisoner
6. Currently involved in a workers' compensation case at the time of enrollment

4. Study Procedure

After enrollment, patients will undergo standardized knee radiography, and complete assessments (described below). Size-matched (standard clinical methodology) proximal tibia with meniscus and distal femur allografts from the same donor will be obtained from a tissue bank (Musculoskeletal Transplant Foundation, Edison, NJ) who has licensed the MOPS technology. The medial or lateral femoral condyle will be replaced using our novel instrumentation and technique described above. Tibial plateau-meniscus grafts will be trimmed and used to replace the entire medial or lateral tibial condyle while sparing the attachments of ACL, PCL and respective collateral ligament. The tibial plateau graft will be fixated using commercial available implants used for bone fixation. In the event that the meniscus has been detached from the tibial plateau during graft harvest, the periphery of the meniscus will be sutured to the capsule following standard meniscus transplant procedure.

Patients will undergo controlled post-operative rehabilitation according to standard protocols for osteochondral with concurrent meniscus allografts. .

Range of motion, VAS pain score, SF-12, Tegner score, International Knee Documentation Committee (IKDC) subjective and objective scores, PROMIS Bank v1.2 – Physical Function-Mobility, PROMIS v1.1 – Global Health, PROMIS Bank v1.1- Pain Interference, PROMIS Bank v1.2 – Physical Function and Marx score as well as complete radiographs of the affected knee will be obtained prior to surgery and at 6 weeks, 3 months, 6 months, and 12 months after surgery to evaluate healing, function and evidence for arthrosis[21].

We will document all complications, including joint or incision infection, graft failure, hardware failure, and arthrofibrosis.

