Patients with a VAS pain score >5 beyond 3 months postoperatively or clinical or radiographic evidence for nonunion or graft collapse will undergo MRI of the knee to determine the appropriate clinical course of action.

For all specific aims, data will be compiled and analyzed using descriptive statistics as well as appropriate tests (*t*-Test, ANOVA, rank sum, repeated measures) for significant ($p < 0.05$) differences using SigmaStat. The investigators on the research team have extensive experience in

data analysis and biostatistics and have the full resources of the university's medical informatics and department of statistics available if questions arise.

5. Safety Assessment

Patients will be monitored post-operatively for signs and symptoms indicating that an adverse event has occurred. The investigator will assess the patient for adverse events at scheduled SOC follow-up visits. Any signs and symptoms indicating that an adverse event may have occurred will be treated by the investigator, and the details will be collected for study purposes. The PI will determine whether an adverse has occurred, and if so, will determine if the event meets the submission requirements of the University of Missouri Health Sciences IRB.

Adverse events and serious adverse events are defined below.

Adverse events:

- I. Bleeding
- II. Infection
- III. Pain that is uncontrolled with standard post-operative analgesia protocol

Serious adverse events:

- I. Bleeding that is significant enough to require extended hospitalization or unplanned critical care interventions
- II. Infection that is significant enough to require extended hospitalization or unplanned critical care interventions
- III. Pain that is significant enough to require extended hospitalization or unplanned critical care interventions

6. Confidentiality of Data

Patient confidentiality during the course of this study will be protected in compliance with HIPAA requirements as well as the requirements of the University of Missouri Health-Sciences IRB.

After consent is obtained, all subjects will be assigned a study identification number that requires the use of a key in order to decipher a subject's personal identification information. The study identification number will be used to label all paper data collection instruments.

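### Section 5 defines adverse events as bleeding, infection and pain only, so three of the four complications the protocol names have no safety classification of their own

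*Combined protocol and SAP*

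**What the plan says.** The objective in Section 2 is "Evaluate safety and efficacy of unicompartmental biologic arthroplasty of the knee in a limited clinical trial". The same section promises: "We will document all complications, including joint or incision infection, graft failure, hardware failure, and arthrophibrosis". Section 4 (Study Procedure) repeats the promise with the same four items. It also provides that patients with "clinical or radiographic evidence for nonunion or graft collapse will undergo MRI of the knee to determine the appropriate clinical course of action".

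Section 5 (Safety Assessment) opens its lists with "Adverse events and serious adverse events are defined below". Three adverse events follow: bleeding, infection, and "Pain that is uncontrolled with standard post-operative analgesia protocol". Three serious adverse events follow in turn, each a more severe form of one of those. The infection item, for example, reads "Infection that is significant enough to require extended hospitalization or unplanned critical care interventions". The items for bleeding and pain use the same threshold.

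On reporting, Section 5 says: "The PI will determine whether an adverse has occurred, and if so, will determine if the event meets the submission requirements" of the university's IRB.

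**The concern.** The two parts of the protocol use different kinds of wording. Sections 2 and 4 are open: they cover all complications and give four as examples. Section 5 is definitional: it has three items, no word marking them as examples, and no category for other events. Nothing in the text connects the complications record to the Section 5 definitions.

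The IRB decision in Section 5 is conditional. The principal investigator first decides whether an adverse event has occurred, and only then considers submission. An event outside the definition has no stated route to that second step.

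The events left out are the ones most specific to this intervention. Section 4 describes replacing a femoral condyle and a tibial plateau with its meniscus by donor tissue, using novel instrumentation, and fixing the tibial graft with implants. Bleeding, infection and pain can follow any operation, whereas failure of the graft or its fixation is particular to this one. With ten patients in the study, each patient is 1/10, or 10 percentage points, of any per-patient safety rate. One unclassified event would therefore visibly change the safety result.

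**Working it through.** No formula applies. The check compares the lists, and the protocol gives no figure of its own to reproduce.

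**Step 1: match the named complications (Sections 2 and 4) to the Section 5 definitions.**

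| Named complication | Adverse event list | Serious adverse event list |
|---|---|---|
| Infection (joint or incision) | yes | yes, if the threshold is met |
| Failure of the graft | no | no |
| Failure of hardware | no | no |
| Arthrofibrosis | no | no |

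Named complications: 4. On the Section 5 lists: 1. Outside both: 4 − 1 = 3.

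In the other direction, bleeding and uncontrolled pain are on the adverse event list but are not among the named complications. The two records share only infection.

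**Step 2: look for other text that closes the gap.**

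- The MRI provision in Sections 2 and 4 covers nonunion and graft collapse. It leads to imaging and a clinical decision, and it assigns no adverse event status or seriousness. These two are not added to the count of three, because the protocol does not define graft failure and they may be forms of it.
- The study activity table, as it can be read, has no row for adverse events or complications. This carries little weight, because the table also lacks a row for the Marx score, which Sections 2 and 4 require.
- No sentence elsewhere links the complications record to Section 5 or to the IRB step.

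**Step 3: apply Section 5 as written to three hypothetical cases.**

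- A graft collapse is seen on a scheduled radiograph, without bleeding, infection or uncontrolled pain. It is recorded as a complication and goes to MRI. It matches no adverse event item, so the condition for the IRB step is not met.
- Hardware fails and the patient is readmitted, again without any of the three listed events. The serious event threshold is attached only to bleeding, infection and pain, so this matches no serious item.
- A patient dies from a cause that did not come through one of the three listed events. This too matches neither list.

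**Step 4: size.** The share of named complications left out is 3 of 4. The number of patients affected cannot be derived, because the documents give no expected complication rate for this procedure.

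**The case against.** The strongest reply is that the Section 5 list need not be read as exhaustive. It does not say that only these events count. The same section has details collected whenever an adverse event may have occurred, and it leaves the determination to the principal investigator. A failed graft will often present as pain or infection and so enter the list through the symptom. The complications are recorded in any case, no adverse event table is specified, and the IRB's own rules may require submission. A small pilot could also reasonably keep procedure-specific complications in one record and general postoperative events in another, in which case one linking sentence would be enough.

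Much of this stands, and it limits the claim. Data capture is not in question. Some graft or hardware failures would gain adverse event status through a symptom, and nothing here shows that events would go unreported to the IRB. The example of a death follows from a strict reading of the definitions; it is not a conflict between two passages.

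It does not remove the point. The lists are called definitions and have no catch-all, so the strict reading is the more natural one. If the investigator has to go beyond the written definition to classify a failed graft, the definition needs correcting. An event that enters as pain would be classed as pain, and one found on a radiograph without a listed symptom would not enter at all. A linking sentence alone would restore the connection, but the seriousness criteria would still apply to only three types of event.

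**Conclusion.** The concern holds. As written, 3 of the 4 complications that the protocol names (failure of the graft, failure of hardware, and arthrofibrosis) are outside both the adverse event and the serious adverse event definitions. They have no seriousness grading and no stated link to the IRB step. Nonunion and graft collapse likewise have no stated safety classification.

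The conclusion rests on reading the Section 5 lists as definitions, which is what the section calls them, and on the absence of any linking text elsewhere. It does not depend on the activity table or on the example of a death.

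The consequence is for how safety is summarised. A table of serious events built on Section 5 could be empty while the complications record showed failed grafts. This does not invalidate the study, because the events are captured. It should be corrected, because the pilot is meant to assess safety and Section 2 foresees a multi-centre trial if the first ten patients do well.

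**What to change.** Reconcile Sections 2, 4 and 5 by changes of wording:

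1. Present the three items in Section 5 as examples of adverse events, not as the full definition.
2. State that every documented complication, including nonunion, graft collapse and death, is classed as an adverse event and assessed for seriousness and for IRB submission.
3. Judge seriousness by the outcome of the event, whatever its type, so that the criteria no longer apply only to bleeding, infection and pain.

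This concerns classification and reporting only and leaves clinical management unchanged. It needs no extra visits. The principal investigator has slightly more classification work, and the reported adverse event rates may look less favourable.

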This proposal stems from the critical clinical need for more optimal treatment options for the millions of young to middle-aged, active patients with damaged knees. Our team, comprised of clinicians and basic scientists, has developed methods to address the current limitations in restoring these patients to high level function. We subscribe to the “joint as an organ” philosophy and have used this philosophy to develop biologic solutions to articular disorders through a collaborative and comparative translational approach. The proposed research will allow us to move these solutions further forward in successfully treating traumatic joint injury in soldiers, civilians, and their four-legged companions.

Rationale: Prior to widespread clinical use, the safety and efficacy of our unicompartmental biologic arthroplasty must be confirmed in a controlled clinical trial. Clinical patients (n=10) with unicompartmental post-traumatic knee OA will be treated with unicompartmental biologic knee arthroplasty and evaluated for functional outcomes.

Based on our preliminary studies and long-term outcomes in clinical veterinary patients, we are optimistic that the final technique for unicompartmental biologic knee arthroplasty that is optimized in specific aim 1 will prove to be vastly superior to non-surgical management of knee OA in the translational model described in specific aim 2. We are confident that clinical use of this technique in specific aim 3 will be safe based on our previous work in conjunction with current evidence regarding clinical use of allografts. If efficacy is as high as expected in the first 10 patients, we will initiate a multi-center clinical trial to include military bases while we continue to follow all patients long term.

3. Selection of Subjects

With IRB approval and informed consent, patients (n=10) (18-50 years old) with post-traumatic knee OA and requiring a tibial plateau and meniscus arthroplasty plus a femoral condyle arthroplasty will be enrolled in the study. Primary criteria for inclusion will be Grade IV changes in the articular cartilage of the femoral condyle and tibial plateau and meniscal pathology in the medial or lateral femorotibial joint as determined by physical examination, diagnostic imaging and knee arthroscopy by the PI. Exclusion criteria include Grade III or IV changes in any other compartment of the knee, acute injury to any other part of the affected lower extremity, or inability to comply with the protocol.

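### Section 5 grades an event as serious only if it needs extended hospitalization or unplanned critical care, so serious harm after discharge can be recorded as non-serious

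*Combined protocol and SAP*

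**What the plan says.** Section 5 (Safety Assessment) introduces its lists with the statement "Adverse events and serious adverse events are defined below". Three event types are listed as adverse events: bleeding, infection, and pain not controlled by the standard analgesia protocol. The same three types form the SAE list, and each is raised to serious by identical wording:

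- "Bleeding that is significant enough to require extended hospitalization or unplanned critical care interventions"
- "Infection that is significant enough to require extended hospitalization or unplanned critical care interventions"
- "Pain that is significant enough to require extended hospitalization or unplanned critical care interventions"

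On timing, Section 5 says "The investigator will assess the patient for adverse events at scheduled SOC follow-up visits" and gives no end date. Section 4 (Study Procedure) schedules outcome scores and radiographs "prior to surgery and at 6 weeks, 3 months, 6 months, and 12 months after surgery".

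Three other provisions bear on the point:

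- Section 5 has details collected for any sign or symptom of a possible adverse event.
- Section 5 has the principal investigator judge each event against the IRB's submission requirements, which are not tied to the SAE list.
- Sections 2 and 4 promise a record of all complications, naming infection of the joint or incision, failure of the graft or hardware, and arthrofibrosis.

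**The concern.** The SAE lines are presented as definitions, not as examples, and nothing else in the document supplies a general test of seriousness. The hospitalization criterion fits the surgical admission, because a stay that is extended is most naturally one already under way. Most scheduled assessments, however, will normally fall after discharge.

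Suppose a patient goes home, develops a joint infection at week 5, is readmitted briefly to an ordinary ward, has a surgical washout and is discharged. On the natural reading no stay was extended and no critical care was used, so the event is an adverse event but not an SAE. A listed event that ends in lasting disability, or in death without critical care or a prolonged stay, has no clear route to SAE status either.

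Safety is part of the stated purpose: "a limited pilot study will be performed to assess safety and efficacy of biologic unicompartmental arthroplasty". If two investigators can grade the same event differently, or a literal reader must grade a reoperated joint infection as non-serious, the SAE count does not describe serious harm reliably.

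**Working it through.** The plan gives no SAE rate, safety margin or derivation of the sample size, so there is no figure of its own to reproduce. The check has two parts.

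**1. Outcomes set against the Section 5 criteria.** The events considered are those on the list (bleeding, infection, pain).

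| Outcome of a listed event | Serious under Section 5 as written? |
|---|---|
| Surgical stay prolonged | Yes |
| Unplanned critical care at any time | Yes |
| Short readmission to an ordinary ward | Unclear; depends on what extended means |
| Unplanned reoperation without a prolonged stay or critical care | Not named |
| Threat to life without a prolonged stay or critical care | Not named |
| Persistent disability | Not named |
| Death without a prolonged stay or critical care | Not named |

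Two rows are clear, one is ambiguous and four have no stated criterion. The complication record in Section 4 would show that an infection occurred, but it carries no seriousness grade and is not linked to Section 5.

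**2. What one regraded patient does to the SAE proportion.** The input is n = 10 in a single treated group, from Section 2: "Clinical patients (n=10) with unicompartmental post-traumatic knee OA will be treated with unicompartmental biologic knee arthroplasty". Intervals are exact (Clopper-Pearson), two-sided 95%.

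- 0/10: the lower limit is 0. The upper limit is 1 − 0.025^(1/10) = 0.3085, giving 0 to 30.8%.
- 1/10: the lower limit is 1 − 0.975^(1/10) = 0.0025. The upper limit solves (1 − p)^10 + 10p(1 − p)^9 = 0.025, so p = 0.445. This gives 0.3 to 44.5%.
- 2/10: 2.5 to 55.6%, by the same method.

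Each patient regraded adds 1/10 = 10 percentage points, provided that patient has no other SAE. The total number of adverse events does not change.

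**How likely is at least one affected patient?** The documents give no rate, so this is illustration only. For an assumed per-patient rate p of post-discharge events that are serious by readmission, reoperation or death, the chance that at least one of 10 patients is affected is 1 − (1 − p)^10:

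- p = 5%: 1 − 0.95^10 = 40%
- p = 10%: 1 − 0.90^10 = 65%
- p = 20%: 1 − 0.80^10 = 89%

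These are chances that such an event occurs. They are upper bounds on the chance of misgrading, because some of these events would qualify through critical care or a prolonged stay.

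**The case against.** The strongest reply is that little is lost. A listed event graded non-serious is still an adverse event with its details recorded. Joint infection is also named in the complication record, and the IRB route works independently of the SAE list. All of this is correct, and it limits the point to classification. It does not remove it: the complication record has no seriousness grade, and an IRB submission does not alter the trial's own SAE classification.

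A second reply is that an investigator could count a readmission as extended hospitalization, and that many reoperations or deaths would involve a long stay or critical care. That is also fair. A reader might infer that Section 5 excludes every readmission, reoperation or death after discharge; the text does not go that far. It is ambiguous on readmission and silent on the others.

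A reader might also try to express the gap as a share of follow-up, treating the hospitalization criterion as available only during the surgical stay. The documents do not support that figure. They give no length of stay, calendar time is not the same as share of events (bleeding and pain can be expected to cluster early), and the critical-care criterion can be met at any time.

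**Conclusion.** The point holds as a defect in the seriousness definition. The criteria in Section 5 are incomplete and one of them is undefined, so serious harm from a listed event can be graded non-serious. Its size is one step of 10 percentage points per affected patient, for example from 0/10 (0 to 30.8%) to 1/10 (0.3 to 44.5%). This assumes that such an event occurs, that it is graded on the narrow reading, and that the patient has no other SAE.

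Two stronger conclusions are tempting but unsupported:

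- **That the trial's 12-month safety result will be understated.** No such result is defined, and no analysis or decision rule uses the SAE count. Section 5 also sets no end date for adverse event assessment; the 12-month horizon comes from the schedule for outcome scores and radiographs.
- **That the next trial would be planned on a faulty SAE rate.** The condition stated in Section 2 for moving to a multi-center trial is efficacy.

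Given the parallel record of complications and the absence of any rule driven by SAEs, this should be corrected, but it ranks below a must-fix. It is best settled before any event is graded, because changing grades afterwards in ten known patients would be open to bias.

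**What to change.** Replace the seriousness wording for all three event types in Section 5 with one set of criteria. An event is serious if it:

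- results in death;
- is life-threatening;
- requires inpatient hospitalization, including readmission, or prolongs an existing stay;
- requires unplanned reoperation on the study knee;
- requires unplanned critical care; or
- results in persistent disability.

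State that the criteria apply from surgery through the 12-month visit. Apply the same grading to the complications documented under Section 4, so that graft failure, hardware failure and arthrofibrosis, which are not on the Section 5 list, also receive a grade and the two records agree.

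The cost is one paragraph in Section 5, a linking sentence in Section 4 and a revision of the adverse event form. No visits, patients or treatments change. The downside is that the reported SAE count may be higher.
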